 the source via ground water, then the recipient should seek information on the extent of the
 contamination plume from the state environmental agency, EPA, and/or the industrial facility.

If the contaminated drinking water is from a municipal system, then the characteristics of the distribution system will be obtained from the water purveyor. If supply wells are used, then the recipient will request historical and current information on these wells including monthly or daily production logs and dates of operation. If a surface water source is used or if water is purchased from another purveyor, then the recipient will request information about this source.

10 The recipient will also request the results of all relevant PFAS sampling: in the surface water near the 11 drinking water intakes, in the distribution system, in the supply wells and nearby monitoring wells, in 12 purchased water from other water purveyors, and in the private wells in the study area.

13

14 **3.10 Statistical Analyses**

15 ATSDR staff will perform statistical analyses with the participation of the recipients using SAS, R and STATA 16 on the combined multi-site study dataset. ATSDR staff may also use SPSS for data management. ATSDR 17 staff will calculate descriptive statistics (including means, geometric means, medians, standard deviations, 18 and percentiles) to identify the presence and distribution of PFAS and effect biomarker analytes. Statistical 19 methods will include multiple linear regression of continuous (untransformed and natural log transformed) effect biomarkers on continuous (untransformed and natural log transformed) PFAS serum 20 21 levels and categorized PFAS serum levels, and logistic regression of categorized effect biomarkers (e.g., 22 hypercholesterolemia) or disease prevalence on continuous (untransformed and natural log transformed) 23 and categorical PFAS serum levels. ATSDR staff will use restricted cubic spline methods (or generalized 24 additive models using cubic regression splines) for linear and logistic regression to obtain flexible, 25 smoothed exposure-response curves. To identify risk factors that may act as confounders for a particular health outcome, the analysis will implement a "10% change in the estimate" rule (Maldonado 1993). 26

Primary analyses will focus on estimated cumulative PFAS serum levels. Supplemental analyses will
evaluate PFAS serum levels in the blood specimens obtained in the study as well as estimated maximum
and average PFAS serum levels. The primary analyses will evaluate each PFAS chemical separately; sum

of PFAS measures may also be considered. Statistical analyses using prevalent cases in a cohort design 1 2 which takes into consideration the times of diagnosis will also be conducted. ATSDR will explore the use 3 of methods for evaluating multi-pollutant mixtures, such as the hierarchical Bayesian model, to analyze 4 the effects of exposures to the PFAS mixtures. ATSDR will use quantitative methods to assess the impact 5 of possible selection bias and possible confounding due to unmeasured risk factors (Lash 2009). There 6 are several caveats and recommendations in conducting analyses of mixtures to determine the optimal 7 method that avoids amplifying bias due to confounding (Weisskopf et al 2018). For the bias analyses, ATSDR will identify "negative control" diseases with no known association with PFAS exposures (Lipsitch 8 9 2010). ATSDR conducted a literature search to identify these negative control diseases and included them 10 in the questionnaire.

ATSDR will interpret the findings from this study based on the magnitude of the effect estimates (e.g., the linear regression coefficient for continuous outcomes or the odds ratio for categorical outcomes) of the exposure-response relationship, consistency with findings from other studies, and the possible sources of bias (Rothman 2014). The analyses will construct confidence intervals to indicate the level of precision (or uncertainty) in the effect estimates.

The studies will use statistical significance testing to interpret findings but will not use it as a sole factor in determining scientific and public health significance (Rothman et al. 2008, 2010; Stang et al. 2010). A finding that fails to achieve statistical significance can still provide evidence for a causal association, and a finding that achieves statistical significance can lack any such significance (Porta 2014).

20 4. RESULTS REPORTING

21 4.1 Notification of Individual Results

22 Some of the clinical tests may include results that indicate disease or serious medical condition. Due to 23 the scheduled timespan between blood specimen collection and the actual laboratory analyses, we are 24 unable to report study results in a short period. Study staff will report to the participant the result of a 25 clinical test that clearly indicates the potential for a serious health consequence immediately after 26 receiving the result from the laboratory. An advance notification phone call from the study investigators 27 (Attachment 22) with a subsequent letter of clinical tests results will be sent to the participant when the 28 abnormal result are identified, processed, and checked for accuracy (Attachment 22a). Study staff will 29 advise the participants to consult his/her physician, or to contact the physician associated with the study 30 for explanation of clinical findings.

Participants will also receive results of their effect biomarker tests after the study is completed. Contract labs will provide their clinical reference abnormal or 'high' levels, if available, for interpretation of clinical test results (Attachment 23). Participants will receive their PFAS test results. The recipient will provide to the 50th and 95th percentiles from NHANES for comparison to the U.S. population (CDC, 2018). Study staff will advise participants to consult ATSDR with questions about their results if they wish to do so.

6 **4.2 Disseminating Results to the Public**

7 The recipient will consult with the local and/or state health agency, local community groups, and the 8 National PFAS Contamination Coalition to determine the most effective method of disseminating the 9 results to the participants and the public. If the recipient establishes a community assistance panel (CAP) 10 in the study area, then the CAP will participate in study community outreach and recruitment activities as 11 well as provide advice on effective methods of results dissemination.

12

The recipient may consider using a user-centered digital interface developed by the Silent Spring Institute for reporting results to each participant. The recipient will present study results to the community in public meetings, printed community handout materials, participating in local radio programs and in informal activities. The recipient also will provide a study website with information about the study findings and general information about any future follow up studies.

Generally, ATSDR will publish study results only as group data analyses in peer-reviewed scientific journals or government reports. If individual data are presented, those will not be linked to participants' identities. In the event that some other exceptional characteristics would enable personal identification, those would be masked or modified as needed to protect individual privacy. ATSDR will use manuscripts published in peer-reviewed scientific journals and presentations at major scientific meetings to inform the scientific community about the results of the Multi-site studies.

24 **5. STRENGTHS AND LIMITATIONS**

Cross-sectional studies are especially suitable for assessing effect biomarkers and the prevalences of nonfatal diseases, in particular, diseases with no clear point of onset (Checkoway 2004). However, if the cross-sectional study concurrently measures the exposure and the outcome (i.e., the disease or effect biomarker), it might be difficult to determine whether the exposure caused the outcome or whether the

outcome influenced the measured exposure level (Flanders 1992, 2016). For example, as discussed above, 1 2 the concurrent measurement of serum PFAS levels and kidney function biomarkers might raise the 3 question of "reverse causation" because kidney function can affect the levels of PFAS in serum. One approach to minimize the problem of reverse causation or possible confounding due to health outcomes 4 5 that affect PFAS serum levels is by estimating exposures based on the historical reconstruction modeling 6 of serum PFAS levels. In addition, it might be possible to estimate exposures during critical vulnerable 7 periods (e.g., in utero exposure) through the modeling of historical serum PFAS levels. However, the 8 modeling of historical PFAS serum levels is subject to uncertainties and data limitations, and published 9 methods currently are available only to model serum levels of PFOA and PFOS.

10 Other issues concerning cross-sectional study designs are similar to those that confront other 11 observational study designs, such as cohort studies. These issues include: 1) the ability to clearly define, 12 enumerate and recruit (without introducing selection bias) the exposed and comparison populations, 2) the comparability of the exposed and comparison populations on risk factors other than the PFAS 13 14 exposures, 3) accurate exposure assessment, and 4) accurate measurement of effect biomarkers and 15 ascertainment of diseases. In addition, a bias similar to the "healthy worker survival effect" bias could 16 occur in a cross-sectional study because the study population consists of those who remained in the study 17 area (and, for example, did not leave the study area due to health problems caused by exposure to the 18 PFAS contaminated drinking water). While the resulting cohort is a 'survivor cohort', the studies have 19 shown that the only if survival after incidence differs by exposure level can results be biased (Barr 2015) 20 for the non-fatal and even in the case of fatal disease...

All epidemiological studies of environmental exposures and health outcomes have limitations and uncertainties. Whether a study will find an association between an environmental exposure and health effects is unknown prior to conducting the study. No single study will provide definitive answers to the community about whether their exposures to the PFAS-contaminated drinking water caused their health problems. The ability of the multi-site study to provide useful information will depend largely on the success of recruiting a sufficient number of study participants and obtaining sufficient information on the PFAS contamination to estimate historical PFAS serum levels with reasonable accuracy.

1 6. REFERENCES

- 2 Agency for Toxic Substances and Disease Registry (ATSDR). Feasibility Assessment for Epidemiological
- 3 Studies at Pease International Tradeport. Portsmouth, New Hampshire. November 2017a. Available at:
- 4 https://www.atsdr.cdc.gov/sites/pease/documents/Pease_Feasibility_Assessment_November-
- 5 2017_508.pdf
- 6 Agency for Toxic Substances and Disease Registry (ATSDR). ATSDR's PFAS Exposure Assessment
- 7 Technical Tools (PEATT). Atlanta, Georgia. November 2017b. Available at: on request ATSDR/DCAI
- Alexander BH, Olsen GW. Bladder cancer in perfluorooctanesulfonyl fluoride manufacturing workers.
 Ann Epidemiol. 2007;17(6):471-8.

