12 The Pease feasibility assessment included sample size calculations for a wide range of health related 13 outcomes (ATSDR 2017a). Sample size calculations selected a type 1 (" α error") of .05 and type 2 error 14 ("β error") of .20. The tables present sample sizes per stratum for specific outcomes for children (Table 15 1) and for adults (Table 2). To determine effect sizes that are reasonable to detect, we selected epidemiological studies using NHANES data. For those outcomes not included in NHANES studies, the C8 16 17 studies were used. The C8 results were considered more representative of U.S. populations (e.g., in 18 background disease rates and prevalence of non-PFAS risk factors) than studies conducted in other 19 countries, although the PFOS, and especially the PFOA, serum levels in the C8 studies were higher than 20 might occur at other sites. For outcomes not evaluated by NHANES or C8 studies, it was necessary to use 21 studies conducted in other countries. The total sample sizes for children and adults should allow for the 22 categorization of PFAS serum levels (or cumulative PFAS serum levels) into e.g. quartiles of exposure: 23 reference level, low, medium and high.

Attachment 3 includes additional information and assumptions pertinent to selected health outcomes to
 be studied.

26 3.3.1 Children

For children, **Table 1** (and **Attachment 3a**) provide the sample size calculations for several health outcomes of interest assuming a type 1 (" α error") of .05 and type 2 error (" β error) of .20. It was considered important that a study have a total sample size so that exposures could be categorized into tertiles (i.e., reference, medium, and high) or preferably into quartiles (i.e., reference, low, medium and
high). Per stratum estimates of needed sample size have been calculated based on different prevalence
of outcomes and detected odds ratios or mean difference.

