4 The proposed sample size of 2,000 children (equally of both sexes) is large enough to effectively evaluate 5 many of the health outcomes identified in the Pease Feasibility Assessment literature review and the 6 recent systematic review (Rapazzo 2017) as potentially associated with PFAS in children. The health 7 outcomes and biomarkers studied would include mean difference in total cholesterol (ranging from 156 8 to 637 per stratum), uric acid levels (556 per stratum), estimated glomerular filtration rate (eGFR; 275 per 9 stratum), testosterone (about 400 per stratum) and insulin growth factor-1 (IGF-1; 146 per stratum). 10 Based on our estimations, we would also be able to detect differences in risk for obesity and atopic 11 dermatitis. A sample size of 2,000 children would be larger than many of the PFAS studies that evaluated 12 neurobehavioral outcomes such as IQ and ADHD (Wang 2015, Stein 2013, 2014, Fei 2011, Hoffman 2010, 13 Strom 2014).

An NHANES study of estimated glomerular filtration rate observed statistically significant findings with a total sample size of just under 2,000 children (Kataria 2015). For thyroid function, estradiol, delayed puberty, and asthma, a total sample sizes of 2,000 children may be sufficient, although larger sample sizes would be optimal (Lopez-Espinosa 2011, 2012; Stein 2016).

In summary, a total sample size of ≥2,000 would be sufficient to evaluate a wide range of biomarkers and
 outcomes including lipids (and hypercholesterolemia), uric acid (and hyperuricemia), estimated
 glomerular filtration rate, testosterone, IGF-1, neurobehavioral measures (executive function, attention,
 IQ) and ADHD, rhinitis, and obesity.

Health-related Endpoint	Relevant Study	Observed Effect Size	Assumptions	Sample Size/Stratum α error = .05 β error = .20
Total Cholesterol	Frisbee 2010, C8 Study	PFOS: 5 th vs 1 st quintile Age: <12 vrs 12-18	Mean PFOS serum levels were about 20	+4.6: 637/stratum
(mg/dL)	1,971 boys <12 yrs 2,773 boys 12-18 yrs 1,886 girls <12 yrs 2,520 girls 12-18 yrs	Boys: +6.2 +9.3 Girls: +4.6 +9.4	μg/L. SD for total cholesterol=29.3 mg/dL	+9.3: 156/stratum
High cholesterol		OR = 1.6	Prevalence=34.2%	300/stratum

22 **Table 1.** Sample size estimations for selected health-related endpoints in Child Study (ages 4-17 years)

Thyroid	Lopez-Espinosa 2012,	PFOS, 4 th vs 1 quartile:	Mean PFOS serum	1,080/stratum

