6 For adults, **Table 2** (and **Attachment 3b**) provide the sample size calculations for several health outcomes 7 of interest assuming a type 1 (" α error") of .05 and type 2 error (" β error) of .20. In this exposure based 8 study we assume an appropriate coverage of range of exposures that will enable 9 stratification/categorization to tertiles or quartiles of exposure. Per stratum estimates of needed sample 10 size (e.g. first vs. fourth quartile) have been calculated based on different measures of association such as 11 odds ratios or detected mean difference.

12 The proposed sample size of 6,000 adults (equally of both sexes) is large enough to effectively evaluate 13 many of the health outcomes identified in the Pease Feasibility Assessment literature review. For example, for outcomes like elevated lipids levels (cholesterol) or uric acid, the range of 229 to 660 14 15 participants per stratum (i.e. quartile) or 200 to 550 per stratum, respectively, given observed differences would be needed. That would translate to overall sample size of about 800 to 2,600 participants being 16 sufficient to detect differences at the specified level of precision and power (Steenland, 2009, 2010; Fisher 17 18 2013; Shankar 2011). Similar sample sizes would also be required to compare other common health 19 outcomes such as cardiovascular disease (Shankar 2012). Larger samples sizes would be needed for liver 20 function or osteoarthritis, with a total sample in the range of 3,000 to 4,000 subjects (Uhl 2013; Gallo 21 2012; Steenland 2010).

22 For thyroid disease and thyroid function, a total sample size of 6,000 may be sufficient although probably 23 not optimal. However, NHANES studies of thyroid function and thyroid disease obtained statistically 24 significant findings with total sample sizes considerably less than 6,000 (Melzer 2010; Wen 2013). 25 NHANES studies of liver function also obtained statistically significant findings with total sample sizes 26 considerably less than 6,000 (Gleason 2015; n=4333). For biomarkers of immune function (e.g., immunoglobulins, C-reactive protein and cytokines) and fatty liver disease, there was insufficient 27 28 information to calculate sample sizes. However, a total sample size of 6,000 should be sufficient to 29 evaluate these biomarkers as we assumed similar endpoint differences of those outcomes.

For ulcerative colitis, a sample size of 6,000 might be sufficient if the effect size in the C8 study (i.e.,

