Attachment 3 – Justification for Sample Size Calculations (Supporting information)

- Attachment 3a Child Sample Size Calculations
- Attachment 3b Adult Sample Size Calculations

Sample size calculations were conducted using OpenEpi Version 3.03 (Dean AG, Sullivan KM, Soe MM. OpenEpi: Open Source Epidemiologic Statistics for Public Health, www.OpenEpi.com, updated 2014/09/22). For some health-related endpoints, calculations could not be conducted because of a lack of information in the studies on the parameters needed to make the calculations.

Sample size calculation for mean difference:

$$n_{1} = \frac{(\sigma_{1}^{2} + \sigma_{2}^{2} / \kappa)(z_{1-\alpha/2} + z_{1-\beta})^{2}}{\Delta^{2}}$$
$$n_{2} = \frac{(\kappa * \sigma_{1}^{2} + \sigma_{2}^{2})(z_{1-\alpha/2} + z_{1-\beta})^{2}}{\Delta^{2}}$$

The notation for the formulae are:

$$n_1 = \text{sample size of Group 1}$$

 $n_2 = \text{sample size of Group 2}$
 $\sigma_1 = \text{standard deviation of Group 1}$
 $\sigma_2 = \text{standard deviation of Group 2}$
 $\Delta = \text{ difference in group means}$
 $\kappa = \text{ratio} = n_2/n_1$
 $Z_{1-\alpha/2} = \text{two-sided Z value (eg. Z=1.96 for 95\% confidence interval).}$
 $Z_{1-\beta} = \text{power}$

Where N_2/N_1 is the ratio of the two sample sizes. Then N_2 is simply this ratio multiplied by N_1 . For a type 1 error (or α error) of .05, the $Z_{1-\alpha/2}$ value is 1.96. This calculation is for a two-tailed hypothesis test and equivalent to using a 95% confidence interval to determine statistical significance. For a one-tail test with α =.05, the $Z_{1-\alpha/2}$ in the above equation is replaced by $Z_{1-\alpha}$ and its value is 1.65, equivalent to using a 90% confidence interval to determine statistical significance. For 80% confidence interval to determine statistical significance. The $Z_{1-\beta}$ in the above equation is the Z value for the selected power. For 80% power, $Z_{1-\beta} = 0.84$, for 90% power, $Z_{1-\beta} = 1.28$, and for 95% power, $Z_{1-\beta} = 1.65$. (See Rosner B. Fundamentals of Biostatistics, 7th Edition, equation 8.27, p. 302).

Fleiss JL. Statistical Methods for Rates and Proportions. John Wiley & Sons, 1981.

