From an NHANES study (Stein 2016), the prevalence of current asthma and rhinitis among those aged 12-19 were 10.9% and 25.6%, respectively. For atopic dermatitis, the prevalence for children and adolescents (ages 5-17) is about 12% based on data from the National Health Interview Survey.

Sex hormones and Insulin-like growth factor – 1 (IGF-1)

C8 study of children (Lopez-Espinosa 2016)

a. Testosterone

For PFOS, there was a -6.6% difference in the natural log testosterone among girls (per interquartile range of the natural log of PFOS). Among girls, the median testosterone level was 15 ng/dL with an IQR of <LOD, 21 and the LOD of 10 ng/dL. For the sample size calculation of mean difference, the standard deviation was assumed to be equal for the exposed and unexposed groups and equal to 11.85. (Assuming LOD/2 was the lower limit of the IQR, the range = 21 - 5 = 16. Assuming a normal distribution, dividing 16 by 1.35 converts the IQR to a standard deviation, which equaled 11.85)¹. To obtain the mean difference, the median testosterone level (15 ng/dL) was assumed to be the reference level (i.e., the level among the unexposed). The natural log of the median equals 2.71. A 6.6% decrease equals 2.53. Exponentiating 2.53 equals 12.55. The mean difference is then 15 - 12.55 = 2.45.

Assuming a 95% CI and 80% power, the sample size = 368/group; for a ratio of 2, the sample sizes = 552 and 276.

b. IGF-1

For PFHxS, there was a -2.5% difference in the natural log IGF-1 among boys (per interquartile range of the natural log of PFHxS). Among boys, the median IGF-1 level was 147 ng/mL with an IQR of 116, 187. For the sample size calculation of mean difference, the standard deviation was assumed to be equal for the exposed and unexposed groups and equal to 52.6. (The IQR range was 187 - 116 = 71. Assuming a normal distribution, dividing 71 by 1.35 converts the IQR to a standard deviation, which equaled 52.6)¹. To obtain the mean difference, the median IGF-1 level (147 ng/mL) was assumed to be the reference level (i.e., the level among the unexposed). The natural log of the median equals 4.99. A 2.5% decrease equals 4.865. Exponentiating 4.865 equals 129.7. The mean difference is then 147 - 129.7 = 17.3.

Assuming a 95% CI and 80% power, the sample size = 146/group; for a ratio of 2, the sample sizes = 218 and 109.

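### Section 3.3.1 calls 2,000 children sufficient for outcomes, ADHD most clearly, that fall short of 80% power on Table 1's own per-stratum sizes

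*Protocol*

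**What the plan says.** Section 3.3.1 states that "The proposed sample size of 2,000 children (equally of both sexes) is large enough to effectively evaluate" many of the outcomes identified in the literature. Among those to be studied it lists "uric acid levels (556 per stratum), estimated glomerular filtration rate" and testosterone at about 400 per stratum. Its summary says that "a total sample size of ≥2,000 would be sufficient to evaluate a wide range of biomarkers" and outcomes, and names lipids, hypercholesterolemia, uric acid, hyperuricemia, testosterone, ADHD, rhinitis and others. Thyroid function, estradiol, delayed puberty and asthma get a softer statement: 2,000 might be enough, although more would be better.

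The sizes in Table 1 are per exposure stratum. The strata are to be "tertiles (i.e., reference, medium, and high) or preferably into quartiles". For adults, section 3.3.2 equates stratum with quartile and takes 200 to 660 per stratum to a total: "That would translate to overall sample size of about 800 to 2,600 participants being" sufficient. That is multiplication by four (200 × 4 = 800; 660 × 4 = 2,640). Attachment 3 says of its mean-difference formula: "This calculation is for a two-tailed hypothesis test". Attachment 3a applies it at 80% power, for example "Assuming a 95% CI and 80% power, the sample size = 368/group" for testosterone in girls.

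**The concern.** The child section never carries out the conversion that the adult section does. When it is applied, several outcomes on the sufficient list need more children than are planned, at the effect sizes the protocol itself chose as reasonable to detect. Section 1.1.3 also says that power should be adequate for effects in the range seen in earlier studies. A null result for ADHD or for sex-specific testosterone could then be reported to exposed communities as coming from an adequately sized comparison when, on the protocol's own inputs, it did not.

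**Working it through.** **Inputs.** Two-sided alpha .05 and power .80 (section 3.3; Attachments 3 and 3a). 2,000 children, half of each sex (section 3.3.1), give 500 per quartile, 667 per tertile, 250 per quartile within a sex and 333 per tertile within a sex. Effects, SDs and prevalences are from Table 1 and Attachment 3a. The ADHD odds ratio is poorly legible in the text at hand; it is read as 1.5, which reproduces the stated size.

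**Formulas.**
- Means (Attachment 3, equal groups): n = 2·SD²·(1.96 + 0.8416)²/d². Power = Φ[d/(SD·√(2/n)) − 1.96].
- Proportions (Fleiss, no continuity correction): n = [1.96·√(2·p̄·(1−p̄)) + 0.8416·√(p1(1−p1) + p2(1−p2))]²/(p2−p1)², with p1 the stated prevalence and p2 from the odds ratio.

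**Reproducing Table 1.**
- Cholesterol, SD 29.3: +4.6 gives 637 and +9.3 gives 156. Both match.
- Testosterone: 1.9 with SD 9.63 gives 404; 2.45 with SD 11.85 gives 368. Both match.
- ADHD: p1 = .124, OR 1.5, p2 = .1751 gives 763 (stated 764).
- Hyperuricemia gives 400 (stated 400); high cholesterol 299 (stated 300).
- TT4: 0.17 with SD 1.4 gives 1,065 (stated 1,080), consistent with rounding of 0.17.
- Uric acid: 0.19 with SD 1.19 gives 2 × 1.4161 × 7.849/0.0361 = 616, **not 556**. A difference of 0.20 gives 556.
- Asthma: p1 = .11, OR 1.2, p2 = .1292 gives about 4,500, **not 2,400**. An OR of about 1.28 gives 2,398.

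The method reproduces the other rows checked, so it does not explain the last two.

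**Totals and achieved power.**

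| Outcome | Stated n per stratum | ×4 | ×3 | Power, quartiles | Power, tertiles |
|---|---|---|---|---|---|
| ADHD, OR 1.5 | 764 | 3,056 | 2,292 | 62% | 75% |
| Testosterone, boys only | 404 | 1,616 boys | 1,212 boys | 60% | 72% |
| Testosterone, girls only | 368 | 1,472 girls | 1,104 girls | 64% | 76% |
| Uric acid, +0.19 | 556 | 2,224 | 1,668 | 71% | 83% |
| Cholesterol, +4.6 | 637 | 2,548 | 1,911 | 70% | 82% |
| TT4, 0.17 | 1,080 | 4,320 | 3,240 | 48% | 60% |
| Asthma, OR 1.2 | 2,400 | 9,600 | 7,200 | 15% | 19% |
| Cholesterol, +9.3 | 156 | 624 | 468 | >99% | >99% |
| High cholesterol | 300 | 1,200 | 900 | 95% | 99% |
| Hyperuricemia | 400 | 1,600 | 1,200 | 88% | 95% |

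Two worked examples. Uric acid at 500: 0.19/(1.19·√(2/500)) = 2.525; 2.525 − 1.96 = 0.565; Φ = 71%. ADHD at 500: (.0511·√500 − 0.989)/0.503 = 0.308; Φ = 62%.

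The testosterone rows use 250 and 333 because about 1,000 of each sex are planned. For TT4 and asthma even two groups of the stated size exceed 2,000: 2 × 1,080 = 2,160, a narrow miss, and 2 × 2,400 = 4,800, a wide one.

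**Rhinitis.** Attachment 3a gives a prevalence of 25.6%. There is no Table 1 row, effect size or stated sample size.

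**The case against.** A reader might infer that four times the per-stratum size exceeds 2,000 for testosterone and for lipids generally. It does not. Testosterone gives 1,616 and 1,472, and pooled at 500 per quartile its power would be 88% for the boys' effect and about 90% for the girls'. The shortfall comes from Table 1 sizing the sexes separately while only about 1,000 of each are planned. For lipids only the +4.6 difference fails. That is one age-sex cell (girls under 12, fifth versus first quintile), and +9.3 and high cholesterol fit easily.

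Tertiles are an accepted design, and there uric acid and the +4.6 difference pass. This stands, with a limit: those effects are quartile and quintile contrasts, and a tertile contrast would ordinarily be smaller. Quartiles are also the stated preference.

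The protocol hedges as well. Section 3.3.2 ends by asking that sample size estimates be read cautiously, section 3.10 does not rest interpretation on significance alone, 2,000 is a minimum, and continuous-exposure regressions are planned that this arithmetic does not describe. Thyroid function and asthma are only said to be possibly adequate, and thyroid disease (over 16,000 per stratum) is never called sufficient. These points soften the consequence. They do not repair a sufficiency statement that the adjacent table contradicts, and no power calculation for the continuous analyses is offered in its place.

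Finally, one might conclude that 616 and 4,500 are the right entries. The protocol does not show whether the input or the output is wrong. For asthma, an OR of 1.2 at the 25.6% rhinitis prevalence gives about 2,377, close to 2,400, so a misplaced prevalence is possible too.

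**Conclusion.** The point holds in graded form.
- ADHD misses 80% under both accepted categorisations.
- Testosterone analysed by sex misses it under both; pooled, it would fit.
- Uric acid and the +4.6 cholesterol difference miss it in the preferred quartiles and pass in tertiles only at an unchanged effect.
- TT4 and asthma cannot be called possibly sufficient on Table 1's figures.
- Rhinitis is listed as sufficient without a basis.
- The uric acid and asthma rows do not follow from their printed inputs.

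This does not show that the child study is too small in general: hyperuricemia, high cholesterol and the larger cholesterol difference are adequately covered.

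The powers assume two-group comparisons of equal strata, every child contributing data, an equal sex split, and stated prevalences that apply to the reference stratum. If the 12.4% ADHD prevalence is instead the average of the two compared strata, the need rises to 895 per stratum and quartile power falls to 55%. Uric acid would have 76% rather than 71% in quartiles if the intended difference was 0.20.

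**What to change.** Keep the target of 2,000. In section 3.3.1 and Table 1:
- Add achieved power, or the minimum detectable effect, at 500 per quartile and 667 per tertile, and at 250 and 333 for sex-specific outcomes.
- Remove ADHD, sex-specific testosterone and rhinitis from the sufficient list.
- Qualify uric acid and the smaller cholesterol difference as below 80% power in quartiles.
- State that TT4 and asthma are underpowered at the listed effects.
- Reconcile the uric acid and asthma inputs with their stated sizes; if the printed inputs stand, the sizes become 616 and about 4,500.

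The cost is protocol wording and one table column, with no added enrolment. The downside is that the stated power becomes less favourable.
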